9.4.1.3 Definitions of Study Period

Data for regular scheduled visits will be summarized as below.

Visit	Actual Point	Visit Window
Screening	Day -28 to Day -7	-
Baseline	Day -2 to Day 1	-
Week 1	Day 1	-
Week 2 ^{a)}	Day 8 to Day 11	-
Week 3 ^{a)}	Day 15 to Day 18	-
Week X	Week X	Part 1; +3 days
		Part 2; ±3 days

a) The first subject aged 6-17 years and the first subject aged 2-5 years (0-5 years in Japan and Brazil) in Part 2

9.4.1.4 Unscheduled Assessments

In case there are measurements from an unscheduled visit after the first dose of JR-171, measurements at scheduled and unscheduled visits are chronologically presented in the subject list whereas the summary of descriptive statistics by time point will only include measurements at scheduled visits.

9.4.1.5 Handling of Missing Data

If any value is missing at any time point, they will be handled as missing and will not be imputed. If any value is reported as 'Below the limit of quantification' or the value cannot be used for calculations, handling of these data will be determined in a separate document which describes standard of adoption for data and subjects.

9.4.1.6 Imputation of Incomplete Dates

For following subject's baseline characteristics data, in case day or month is omitted thus collected as 'Unknown', these missing date units will be imputed with '1' for calculation of some durations.

- date of diagnosis of MPS I
- · start date of treatment with laronidase
- date of HSCT treatment
- date of measurement of Enzyme activity in leucocytes or cultured skin fibroblasts
- date of measurement of urinary GAG concentration or uronic acid concentration

For concomitant medication and concomitant treatment used after the first administration of JR-171, in case the day is omitted from the start or end date thus collected as 'Unknown', only collected date units will be used without any imputation of the date.

9.4.2 Demographic and Other Baseline Characteristics

Major demographic variables, such as age, sex, country, race, phenotype, and some variables about MPS I related characteristics will be summarized by study period and dose group, by the number and percentage of subjects using descriptive statistics for continuous variables and counts and percentages for categorical variables.

9.4.3 Safety Analyses

This section outlines the planned safety analyses in the JR-171-101 study. Safety analyses will be performed on the SS.

All AEs will be coded to PT and system organ class (SOC) using the latest version of the Medical dictionary for regulatory activities terminology (MedDRA).

All AEs occurred after the first dose of JR-171 will be considered as treatment-emergent AEs and will be summarized by study period and dose group. For each study period and dose group, the incidence proportion of AEs will be summarized with frequency and percentage by MedDRA SOC and PT.

AEs occurring before the first dose of JR-171, include AEs that occurred in screen failure, will be pooled regardless study period or dose group and summarized in the same way.

For laboratory tests, summary statistics of measured values at each time point as well as changes from baseline will be calculated for Part 1 and each group in Part 2, and time courses

or shift tables will be created for each subject.

For vital signs, summary statistics of measured values at each time point as well as changes from baseline will be calculated for Part 1 and each group in Part 2, and time courses will be created.

For 12-lead electrocardiogram, the presence or absence of abnormality will be tabulated.

For antibody tests, shift tables will be created with respect to the presence or absence of antibody development at each time point.

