1.3 Schedule of Activities

Part 1

Observation/test timing	Pre-screening	Screening test	Registration	Baseline	Week 1	Week 2	Week 3	Week 4	Week 5	Discontinuation
Visit window	-	28 days before Day 1 (Day -28) to Day -7	-	Day -2 to Day 1	Day 1	Day 8 to Day 11	Day 15 to Day 18	Day 22 to Day 25	Day 29 to Day 32	Within 28 days from discontinuation
JR-171 administration					Х	Χ	Х	Χ		
Informed consent	X									
Subject baseline characteristics ^{a)}		Х								
Assessment based on			Х							
inclusion/exclusion criteria			^							
Pregnancy testing (female subjects of childbearing potential only)		X								
Vital signs ^{b)}		Xc)		X _d)	X ^{e)}	X ^{e)}	X ^{e)}	X ^{e)}	X ^{c), f)}	X _{c)}
Laboratory tests ^{f)}		X		X		X	X	X	X	X
Antibodies ^{f)}				X ^{g)}		X ^{h)}			X ^{g)}	X ^{g)}
Plasma drug concentration ⁱ⁾					Х	X	Х	Х		
Drug concentration in CSF				X ^{f)}				X ^{j)}		X ^{k)}
HS and DS concentrations in CSF				X ^{f)}				X ^{j)}		X ^{k)}
CSF opening pressure				X ^{f)}				X _{j)}		X ^{k)}
Urinary HS and DS concentrations (including measurement of creatinine for concentration adjustment) ⁽⁾				х		Х	Х	Х	Х	х
Serum HS and DS concentrations ^{f)}				Х		Х	Х	Х	Х	X
Liver and spleen volumes ^{f)}				Х					Х	Х
Cardiac function ^{f)}				Х					Х	Х
Other clinical findings related to neurocognitive and behavioral changes										
12-lead electrocardiogram ^{f)}		Χ							Х	X
Cross-reactive immunologic material ⁱ⁾										—
AEs										—
Concomitant therapies/medications					Х	Х	Х	Х	Х	Х

- of JR-171.
- b) Vital signs: pulse rate, body temperature, blood pressure, respiratory rate, percutaneous oxygen g) saturation and body weight. During the infusion of JR-171, it is necessary to monitor other than body h) Anti-JR-171 antibodies weight (see Section 6.1 and 8.2.3).
- c) Excluding body weight
- d) Only body weight is measured.
- e) Perform before and after administration of JR-171 except for body weight. Body weight will be measured at either measuring point.
- a) Neurocognitive testing and adaptive behavior assessment will be performed before the first infusion f) Perform before administration of JR-171 (or before laronidase at Week 5, for subjects who will receive laronidase after completing the JR-171-101 study)
 - Anti-IDUA and anti-JR-171 antibodies

 - Blood specimens should be collected by following the "PK sampling schedule (plasma drug concentration)".
 - Performed within 5 hours after the end of administration of JR-171

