8.3 Adverse Events and Serious Adverse Events

In the event of AEs, the safety of subjects is ensured by providing appropriate medical care to subjects.

AEs will be reported by the subject (or, when appropriate, by a caregiver, surrogate, or the subject's legally authorized representative).

The principal investigator and any qualified designees are responsible for detecting, documenting, and recording events that meet the definition of an AE or SAE (Appendix 2 (see Section 10.2.1 and 10.2.3)) and remain responsible for following up on AEs that are serious, considered related to the study intervention or study procedures, or that caused the subject to discontinue the study (see Section 7).

If an AE occurs, the name, severity, seriousness, day of onset, presence or absence of treatment for study treatment, outcome of the AE (including date of assessment), relationship between the AE and investigational product, comments as appropriate, and whether or not with IAR should be recorded in the eCRF.

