8.3.1 Time Period and Frequency for Collecting AE and SAE Information

All AEs and SAEs will be collected from the time of informed consent until the last visit (Week 5 in Part 1/Week 13 in Part 2, or discontinuation) at the time points specified in the Schedule of Activities (see Section 1.3). Events occurring within 28 days after the time of observation at Week 5 in Part 1/Week 13 in Part 2 or discontinuation that are considered related to the investigational product will be collected as adverse drug reactions in the JR-171-101 study, except for events that are occurred during the extension study of the JR-171-101 study (JR-171-102). In the eCRF, presence or absence of AEs and, if applicable, its details (Appendix 2 (see Section 10.2.4)) should be recorded.

Data of MPS I-related medical occurrences that begin before obtaining informed consent will be recorded in the Medical History/Current Medical Conditions section of the case report form not in the AE section.

All SAEs will be recorded and reported to the sponsor immediately and under no circumstance should exceed 24 hours, as indicated in Appendix 2 (see Section 10.2). The principal investigator will submit any updated SAE data to the sponsor within 24 hours of it being available.

Principal investigators are not obligated to actively seek AEs or SAEs after conclusion of the study participation. However, if the principal investigator learns of any SAE, including a death,

at any time after a subject has been discharged from the study, and he/she considers the event to be reasonably related to the study intervention or study participation, the principal investigator must promptly notify the sponsor.

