10.2.1 Definition of AE

AE Definition

An AE is any untoward or unintended illness or its sign (including an abnormality observed in laboratory tests or physiological tests) in a subject, which does not necessarily have to have a causal relationship with the investigational product. AEs that occur after the administration of an investigational product, those that have an undeniable causal relationship with the investigational product are considered adverse drug reactions.

- Any patient having received any amount of investigational product should be evaluated for safety. The schedule of assessments is shown in the Schedule of Activities, Section 1.3.
- Any AE must be documented and the following guidelines will be used for this purpose. An AE is the development of an undesirable medical condition or the deterioration of a pre-existing medical condition following or during exposure to a pharmaceutical product, whether or not considered causally related to the product. An undesirable medical condition can be symptoms (e.g., nausea, chest pain), signs (e.g., tachycardia, enlarged liver) or the abnormal results of an investigation (e.g., laboratory findings, electrocardiogram). In clinical studies, an AE can include an undesirable medical condition occurring at any point of time after the patient consented to participate. This definition includes intercurrent illnesses or injuries, and exacerbation of pre-existing conditions.
- Where a diagnosis is possible, it is preferable to record it in the eCRF rather than as a series of terms relating to the diagnosis.
- An event that is solely due to progression of disease should not be reported as AEs.

Events Meeting the AE Definition

- Any abnormal laboratory test results (hematology, clinical chemistry, or urinalysis) or other safety assessments (e.g., ECG, radiological scans, vital signs measurements), including those that worsen from the time of informed consent, considered clinically significant in the medical and scientific judgment of the principal investigator or subinvestigator (i.e., not related to progression of underlying disease).
- Exacerbation of a chronic or intermittent pre-existing condition including either an increase in frequency and/or intensity of the condition.
- New conditions detected or diagnosed after study intervention administration even though it may have been present before the start of the study.

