10.2.4 Recording and Follow-Up of AE and/or SAE

AE and SAE Recording

- In the event of an AE/SAE, the name of the AE, severity, seriousness, the date of
 occurrence, whether or not there was a procedure for the administration of the
 investigational product as well as its details, the outcome of the AE (including the date of
 its determination), a causal relationship between the AE and the investigational product,
 and comments as needed should be recorded in the eCRF.
- It is the responsibility of the principal investigator or subinvestigator to document any AE
 occurring from the time of informed consent obtained in the subject's hospital notes and in
 the eCRF. MedDRA will be used to code AEs by the data management and
 pharmacovigilance groups.

Assessment of Severity

The principal investigator or subinvestigator will determine the severity of AEs reported on the eCRF as follows:

If the AE is listed in the CTCAE Version 5 table, then the highest level that the AE reached should be noted. If the AE is not listed in the CTCAE Version 5, then the highest level reached should be noted, according to the following description:

Assessment of Severity

- Grade I = Slight: An AE, which is easily tolerated by the patient. It only incurs a
 minimum of discomfort and does not influence ordinary daily tasks.
- Grade II = Moderate: An AE, which is of sufficient severity to have a negative influence on ordinary daily tasks.
- Grade III = Severe: An AE, which effectively hinders ordinary daily tasks.
- Grade IV = Life threatening: An AE, which puts the patient's life at risk.
- Grade V = Death: Death related to AE.

Assessment of Causality

• The principal investigator or subinvestigator are obligated to assess the relationship between study intervention and occurrence of each AE/SAE.

Related: The causal relationship between the investigational product and the AE may be at least reasonable and may not be denied because of disappearance after discontinuation of administration, recurrence after resumption of administration, establishment of a causal relationship with the investigational product or similar drug, absence of confounding risk factors, consistency with exposure and duration of exposure, almost definite explanation for the contribution of the investigational product by supporting an accurate medical history, and lack of reasonable possibility of causal relationship between the concomitant medications/therapies and the AE.

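### The treatment-emergent rule in Section 9.4.3 has no clause for an AE that begins before the first dose and worsens after it, so on-drug worsening can be missed

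*Combined protocol and SAP*

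**What the plan says.** Section 9.4.3 (Safety Analyses) sorts AEs into two classes. The first is treatment-emergent: "All AEs occurred after the first dose of JR-171 will be considered as treatment-emergent AEs and will be summarized by study period and dose group". The second is everything earlier: "AEs occurring before the first dose of JR-171, include AEs that occurred in screen failure, will be pooled regardless study period or dose group". For the treatment-emergent class "the incidence proportion of AEs will be summarized with frequency and percentage by MedDRA SOC and PT", and the pre-dose class is tabulated in the same manner. Neither sentence mentions a change in severity.

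Four other places bear on how an event reaches one class or the other:

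- Section 8.3.1, collection period: "All AEs and SAEs will be collected from the time of informed consent until the last visit".
- Section 8.3, contents of the AE record: "the name, severity, seriousness, day of onset, presence or absence of treatment for study treatment", followed by outcome, relationship and an IAR flag.
- Section 10.2.4, grading: "If the AE is listed in the CTCAE Version 5 table, then the highest level that the AE reached should be noted". Events not listed in CTCAE are handled likewise.
- Section 10.2.1, events that qualify as AEs: "Exacerbation of a chronic or intermittent pre-existing condition including either an increase in frequency and/or intensity of the condition".

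Frequency and severity of AEs is the first endpoint listed under the primary objective in Section 3.

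**The concern.** The usual definition of a treatment-emergent event has two limbs: onset after first exposure, or worsening after first exposure. Section 9.4.3 has only the first. The second matters when AEs are collected before dosing begins, as they are here.

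The pre-dose period is not short or empty. Consent comes before screening, and the Part 1 screening window is "28 days before Day 1 (Day -28) to Day -7"; Part 2 uses the same days. Each subject also has a baseline lumbar puncture before the first infusion, in the window Day -2 to Day 1 (Sections 1.3 and 8.5.1), under sedation or general anaesthesia (Section 8.5.2). Section 2.3.1 names headache and vomiting as possible reactions to JR-171. The documents do not say that the puncture can cause the same symptoms; I assume it can.

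If worsening of an open AE is kept on the existing record, that record has a pre-dose onset. The on-drug deterioration then disappears from the summary by study period and dose group, which is the one used to judge tolerability in a first-in-human trial.

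**Working it through.** The plan gives no figure on this point, so there is none to reproduce. The check sets the rules side by side on one hypothetical case, then works out direction and size.

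**Case.** Headache starts at grade I on Day -1, after consent, and reaches grade III after the first infusion.

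| Recording convention | Record(s) produced | Result under Section 9.4.3 |
|---|---|---|
| Worsening updates the open record | One AE, onset Day -1, highest grade III | Pre-dose pool, no dose group; not treatment-emergent |
| Worsening is a new AE | AE 1: onset Day -1. AE 2: onset after first dose, grade III | AE 2 is treatment-emergent, in its dose group |

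**Which convention applies?** Three provisions lean towards the first row: a day of onset is recorded for each AE (Section 8.3), the highest grade is noted (Section 10.2.4), and the event is followed until it returns to the baseline grade or to grade I or lower (Section 10.2.4). Section 10.2.1 leans towards the second, since it counts deterioration following exposure as an AE in its own right. That section says what qualifies as an AE; it does not say how an AE already on file is split. No section settles the choice, and with six planned sites in three countries the same event could be recorded either way.

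**Direction.** Let A be the AEs with onset after the first dose, and B the AEs with onset or grade increase after it. Every member of A is in B. The number of subjects with at least one event of a given preferred term is therefore no greater under A than under B. The missing clause can lower treatment-emergent incidence or leave it unchanged; it cannot raise it.

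**Size of one missed subject.** Change in incidence = 1/n. This takes n as the treated subjects in the group and assumes the subject has no other post-dose event of that preferred term.

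- Part 1: n = 4 (Section 9.2), so 1/4 = 25.0 percentage points.
- Part 2 randomized group: n is at least 6 (Section 4.1), so at most 1/6 = 16.7 points. With about 15 enrolled and 2 in dose escalation, 15 - 2 = 13, which splits as 6 and 7; for the larger group 1/7 = 14.3 points.
- If the subject has another post-dose event of the same preferred term: 0 points.

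**How often.** The documents give no rate of AEs open at the first dose and no rate of worsening among them. No probability of occurrence can be derived.

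**The case against.** The strongest reply is that Section 10.2.1 already closes the gap. If deterioration following exposure is an AE, it is an AE that occurred after the first dose, and Section 9.4.3 makes it treatment-emergent. This stands as a possible reading, and it shows what the authors intended. It does not stand as a rule, because nothing tells a site to open a second record.

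Three stronger readings may tempt a reader, and the documents do not support them:

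- That such an event is necessarily placed in the pre-dose table at its post-dose grade. The recording convention is unstated, so this is possible but not forced.
- That both planned tables would be wrong. They show system organ class and preferred term without grade. A headache that began before dosing is correctly counted in the pre-dose table; only the treatment-emergent table can lose something. The peak grade would mislead only in a severity summary, which Section 9.4.3 does not describe.
- That incidence is always lowered. It is not when the subject has another post-dose event of the same term.

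It can also be said that the detail belongs elsewhere. Section 9.4 calls itself a summary and announces a fuller SAP, and Section 10.1.15 refers eCRF completion to a separate manual. Neither text is in the document reviewed, and either may settle the convention. They would not alter the definition written in Section 9.4.3, which is the one stated for a primary endpoint.

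Finally, IARs are protected. Their frequency is a separate primary endpoint, defined by timing around each infusion (Section 8.3.6), and the IDSMC consultation in Section 6.6.1 depends on grade III or higher IARs within 24 hours, not on treatment-emergent status. This stands: the gap affects the AE summary, not the escalation safeguards.

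**Conclusion.** The point holds as an incomplete definition with a known direction and an unknown frequency. Section 9.4.3 uses timing alone, and the recording rules leave open whether on-drug worsening of an AE already open ever becomes an event with a post-dose onset. Where it does not, the worsening is missing from the treatment-emergent summary by dose group.

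The per-subject sizes shown above rest on treated subjects being the denominator and on no second post-dose event of the same term. The first needs stating because the safety set in Section 9.3 is everyone who signs the consent form; a denominator that included screen failures would make each step smaller. The change is worth making because the endpoint is primary, the groups are very small, any error runs towards making the drug look better tolerated, and the correction follows the intent already visible in Section 10.2.1.

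**What to change.** In Section 9.4.3, define treatment-emergent AEs as AEs that start, or increase in CTCAE grade, after the start of the first JR-171 infusion, summarized by study period and dose group.

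In Section 10.2.4, state that an AE open at the first dose which then increases in grade is entered as a new record dated at the worsening, and that the existing record keeps its highest pre-dose grade. Existing fields (day of onset, severity, outcome with its date) can carry this.

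Costs:

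- The eCRF completion guidance must change.
- This is version 6.00 of November 2021 and enrolment was planned from September 2020, so any existing records of AEs open at the first dose need checking, and some may need re-entry from source notes.
- A few more events will count as treatment-emergent, some of them possibly procedure-related; the causality assessment already recorded for each AE helps to separate these.

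A grade-based rule does not catch a rise in frequency at constant grade, which Section 10.2.1 also counts as an AE. The recording guidance should say how that is entered.

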8.2.3 Vital Signs

Pulse rate, body temperature, blood pressure (systolic and diastolic blood pressure) respiratory rate, and percutaneous oxygen saturation will be measured before and after administration of JR-171 or laronidase. Body weight will be measured only once at each measurement point. In principle, blood pressure will be measured in the same posture throughout the JR-171-101 study. In the eCRF, whether or not a measurement has been performed as well as the date and time and results of measurement, if performed, should be recorded. When JR-171 is administered, vital signs will be also measured at the end of administration, and the time of measurement as well as the results of pulse rate, body temperature and blood pressure should be recorded in the eCRF.

During infusion of JR-171, the principal investigator or subinvestigator ensure vital signs are taken in a timely manner. Especially, vital signs are recommended to be obtained when infusion rate is increased, and to be obtained at least every 30 minutes while the infusion rate does not change. The measurements during infusion of JR-171 do not have to be recorded in the eCRF, but if AEs occur, the detail of the AEs should be recorded in the eCRF.

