9.4.1.2 Definitions of Baseline

Unless otherwise specified, the baseline value will be defined as the measurement prior to and closest to the date of the first dose of JR-171.

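### Does the vital-signs analysis need a same-day, post-minus-pre-infusion change because the only change planned is from the value before the first dose?

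*Combined protocol and SAP*

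**What the plan says.** Change in vital signs is one of several descriptive primary safety endpoints (sections 1.1 and 3). For its analysis, section 9.4.3 says: "For vital signs, summary statistics of measured values at each time point as well as changes from baseline will be calculated for Part 1". The same sentence extends this to each group in Part 2 and adds time courses.

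The reference value comes from section 9.4.1.2: "the baseline value will be defined as the measurement prior to and closest to the date of the first dose of JR-171". That definition opens with a clause allowing a different reference where one is specified. The vital-signs paragraph specifies none.

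The data collected are richer than one value per visit:

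- The footnote to the infusion visits in section 1.3 reads "Perform before and after administration of JR-171 except for body weight".
- Section 8.2.3 agrees ("percutaneous oxygen saturation will be measured before and after administration of JR-171 or laronidase"). It also requires a reading at the end of each administration, for which the time and "the results of pulse rate, body temperature and blood pressure should be recorded in the eCRF".
- At the Baseline visit itself, section 1.3 says "Only body weight is measured". The last full set of vital signs before dosing is therefore the pre-infusion set on Day 1.

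Section 9.4.1.3 introduces its table with "Data for regular scheduled visits will be summarized as below" and lists visits only, without separating readings within a visit. Section 9.4.1.4 provides for a by-subject list: where there are unscheduled readings after the first dose, "measurements at scheduled and unscheduled visits are chronologically presented in the subject list".

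**The concern.** An intravenous enzyme can move blood pressure, pulse and temperature within hours, and section 2.3.1 names infusion reactions and anaphylactic shock as risks. The natural contrast for such an effect is the reading after an infusion minus the reading before it on the same day. The plan collects both at every infusion but states only a change from the single value before the first dose.

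From the second infusion on, that change has two parts: the acute effect of the infusion, and any drift in the pre-infusion level since Day 1. The reference can be up to 80 days old. If the two parts could not be separated, a real acute effect might be blurred in a primary safety endpoint. This would happen at about nine infusions in ten, although the data to avoid it are already in the database.

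**Working it through.** **1. How many infusions have an earlier-day reference.** Inputs: 4 subjects in Part 1 and about 15 in Part 2 (section 9.2); 4 infusions each in Part 1 and 12 each in Part 2, where the escalation subjects have 3 + 9 = 12 (sections 1.1 and 1.2). Full attendance is assumed, with the Day 1 pre-infusion reading as baseline.

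- All infusions: 4 × 4 + 15 × 12 = 16 + 180 = 196.
- After the first: 4 × 3 + 15 × 11 = 12 + 165 = 177, and 177/196 = 90.3%.
- At the Part 2 minimum of 2 + 6 + 6 = 14 subjects (section 1.2): 4 × 3 + 14 × 11 = 166 of 4 × 4 + 14 × 12 = 184, or 90.2%.

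The documents state neither 196 nor 177. The share is simply one minus the share of first infusions (19/196 = 9.7%). It follows from repeat dosing with one baseline and measures neither bias nor lost signal. For the 19 first infusions, change from baseline already is the same-day change.

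**2. How old the reference is.** From the visit windows in section 1.3, Part 1 infusions after the first run from Day 8 to Day 25, so the Day 1 reading is 7 to 24 days old. In Part 2 they run from Day 8 − 3 = 5 to Day 78 + 3 = 81, so it is 4 to 80 days old.

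**3. Whether the acute effect is lost.** For infusion *k*:

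(post_k − pre_1) = (post_k − pre_k) + (pre_k − pre_1).

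The first term on the right is the acute change and the second is drift. The drift term is itself the planned change from baseline, taken at the pre-infusion reading. If before and after readings are tabulated as separate time points with complete pairs, subtracting the two planned means gives the mean same-day change exactly. The SD of the individual same-day changes is not in a planned summary, but each one can be computed from the recorded readings.

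**4. What a same-day table would gain in precision.** Suppose a reading varies between days with SD *r* times the within-session SD. The SD of change from Day 1, relative to the same-day SD, is then √(1 + r²). For assumed *r* = 0, 0.5, 1 and 2 this is 1.00, 1.12, 1.41 and 2.24. The documents give no value for *r*, so the gain may be nil.

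**5. What that table would look like.** The cells per variable are 4 doses in Part 1 plus 2 × 12 group-weeks = 28, or 4 + 3 × 12 = 40 with the escalation subjects shown separately. There would be 6 post-minus-pre variables (systolic and diastolic pressure counted separately) and 4 end-minus-pre variables, giving 28 × 10 = 280 to 40 × 10 = 400 cells. Each would hold 4 subjects in Part 1, about 6 to 7 per randomised group, or about 2 in escalation. The 95% half-width for a mean, t(0.975, n−1)/√n, is 3.182/2 = 1.59 SD at n = 4 and 2.571/2.449 = 1.05 SD at n = 6.

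**6. Where acute effects are captured.**

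- Frequency of infusion associated reactions is a separate primary endpoint (sections 1.1 and 3). Section 8.3.6 defines them as arising during the infusion or within 24 hours of its end, and its examples include fever and high blood pressure.
- Section 8.3 has each adverse event recorded with whether it was such a reaction.
- Section 10.2.1 makes a clinically significant abnormal vital sign an adverse event.
- Dose escalation rests on investigator judgement, sponsor approval and, for severe reactions, consultation of the independent committee (section 6.6.1), not on these tables.
- Section 9.1 plans no hypothesis test for safety.

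**The case for a change.** The strongest case for adding the contrast is that it costs one derived variable and one table, needs no new data, and matches the time scale of the risk. The adult hypotension criterion in section 8.3.6 itself looks at a drop from the last measurement, not from study baseline. The Day 1 reading may also be untypical, because the pre-dose lumbar puncture falls between Day −2 and Day 1 and is done under sedation or general anaesthesia (sections 1.3 and 8.5.2).

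Two points of wording are also open. Section 9.4.1.3 does not say whether before, after and end-of-administration readings count as separate time points. Section 9.4.1.2 refers to the date of the first dose; read strictly, this could point back to screening. The reference would then be 7 to 28 days old at the first infusion and 7 + 4 = 11 to 28 + 80 = 108 days old later, and all 196 infusions would be affected.

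The contrast is reasonable and the open wording is real. But the same-day contrast is not a clean measure of the acute effect either. Pretreatment is allowed, and a reaction may be met by slowing, interrupting or treating (section 6.1), so the later reading may reflect that treatment. At Week 4 in Part 1 and Week 12 in Part 2, lumbar puncture within 5 hours after the infusion may overlap the post-infusion reading. Changes that appear and resolve during the infusion are missed by both contrasts, since those readings need not be entered (section 8.2.3).

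The screening reading of the baseline rule is strained: the Day 1 pre-infusion set is plainly the closest before dosing. Labels for time points and the vital-sign baseline are details for the separate, more technical SAP announced in section 9.4, which is not among the documents and may already hold them.

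**Conclusion.** The concern does not hold. Change from study baseline is a valid descriptive summary of vital signs. It is planned together with measured values and time courses, from readings that include before, after and end-of-administration values. Acute infusion reactions are captured and reported through their own primary endpoint.

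The figure of 177 of 196 infusions (90%) is correct for 4 + 15 subjects at full attendance with the Day 1 pre-infusion reading as baseline. It says only that most infusions are not the first. No bias, missed signal or altered decision follows from it, and any gain in precision is unknown and may be nil. A same-day table would be a matter of preference, in small cells with wide intervals.

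This conclusion assumes that the before and after readings are recorded as sections 1.3 and 8.2.3 require. It does not depend on the separate SAP containing the contrast.
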